## 5 DATA HANDLING CONVENTIONS

All data collected in the study will be listed.

### 5.1 General Data Reporting Conventions

For continuous variables, the following summary statistics will be provided: number of subjects, mean, standard error (SE) of the mean, standard deviation (SD), minimum, maximum, and median. Unless specified otherwise, means, medians, and confidence intervals (CIs) will be presented to one more decimal place than the raw data, and the SDs and SEs will be presented to 2 more decimal places than the raw data. In general, the maximum number of decimal places is 4 and values will be truncated to 4 decimal places in situations where there are more than 4 decimal places. Wherever possible data will be decimal aligned.

For categorical variables, summaries will include the number and percentage of subjects in each category; the number of subjects and the percentage of subjects with missing data will be summarized for demographic and baseline characteristics (if applicable). Categories with zero counts will not have zero percentages displayed. Percentages will be presented to 1 decimal place. For demographic (except for Childbearing Potential) and baseline summaries (except for NPI-Q distress), percentages will be calculated by using the total number of subjects as the denominator.

Unless specified otherwise, all statistical tests will be 2-sided hypothesis tests performed at the significance level of 0.05 for main effects. All CIs will be 2-sided, 95% CIs, p-values will generally be presented to 4 decimal places, and p-values less than 0.0001 will be presented as <0.0001

Values that are collected with “<” or “>” signs will generally be analyzed as the numerical value without the sign in tables and figures. In listings, these data will be reported as collected with the sign.

Duration in months will be calculated as (number of days/365.25)\*12 and will be rounded to 1 digit after the decimal point (tenths) for presentation purposes.

Duration in years will be calculated as number of days/365.25 and will be rounded to 1 digit after the decimal point (tenths) for presentation purposes.

Baseline is defined as the last non-missing value prior to the first dose of study drug. All change from baseline endpoints are calculated as the value of the corresponding post-baseline visit minus the value at baseline.

## 5.2 Derived Efficacy Variables

In general, all assessment scale total scores and subscores will be derived within the analysis datasets (with the exception of the VRFCAT variables, which are derived by the VRFCAT software). In the event that total scores and/or subscores are also collected on the eCRF, the derived values will be used for all analyses. Both the raw and derived scores will be presented in data listings.

### 5.2.1 Mini-Mental State Examination

The Mini-Mental State Examination (MMSE) is assessed only at the Screening visit. The MMSE is being used in this study to screen for cognitive impairment.

The MMSE is a 30-item questionnaire that includes simple questions and problems in the following areas: time and place of testing, repeating lists of words, arithmetic, language use and comprehension, and copying or drawing.

Each of the 30 items is scored as 0 for an incorrect response, and 1 for a correct response. The MMSE total score will be derived as the sum of the 30 item scores; thus, the total score has a potential range of 0 to 30. Lower scores indicate more severe cognitive impairment.

The total score will be set to missing if there are one or more missing items.

### 5.2.2 NPI Domains A and B

At Screening (Visit 1) and Baseline (Visit 2), the degree of the patient's neuropsychiatric symptoms will be evaluated using two of the domains of the Neuropsychiatric Inventory (NPI), Domain A (Delusions) and Domain B (Hallucinations). For each domain, three separate ratings are collected, Frequency, Severity and Distress, and are scored as follows:

- Frequency of the symptom: 0=no symptom, 1=occasionally, 2=often, 3=frequently, 4=very frequently
- Severity of the symptom: 0=no symptom, 1=mild, 2=moderate, 3=severe
- Distress (how it affects the caregiver): 0=no distress, 1=minimal, 2=mild, 3=moderate, 4=severe, 5=extreme or very severe

The individual domain scores are calculated as the frequency score  $\times$  severity score. The NPI psychosis score is derived as the sum of the domain A and domain B scores. If either A or B domain scores are missing then the psychosis total score will be missing.

Missing NPI scores (frequency, severity, and distress) will not be imputed. However, each of the individual domains contains a screening question that is used to elicit whether the

symptom is present or absent. If the answer to the screening question is “No” then the derived domain score will be set to 0.

### **5.2.3 NPI-Q Nighttime Behavior Domain**

The NPI-Q is a self-administered questionnaire completed by informants about patients for whom they care. In this study, the informant is typically the caregiver. There are 12 domains in the full questionnaire; however, only the Nighttime Behavior domain will be completed by informants in this study. Two separate ratings are collected, Severity and Distress, and are scored as follows:

- Severity of the symptom (how it affects the subject): 0=no symptom, 1=mild, 2=moderate, 3=severe
- Distress (how it affects the informant): 0=not distressing at all, 1=minimal, 2=mild, 3=moderate, 4=severe, 5=extreme or very severe

If the informant reports that nighttime behaviors are not present, the Severity score will be set to 0, and the Distress score will remain a missing value. Otherwise, missing Severity and Distress scores will not be imputed.

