## 12 EFFICACY ANALYSES

All efficacy analyses will be performed using the Full Analysis Set. Descriptive summaries of all efficacy endpoints will be provided. No hypothesis testing is planned.

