### 12.3 Exploratory Efficacy Endpoints

The exploratory efficacy endpoints are the following:

- Change from Baseline to Week 16 on the VRFCAT including adjusted total time T-score, total number of errors T-score, and total number of forced progressions T-score
- Change from baseline to Week 16 on the CSI total score
- Change from Baseline to Week 16 on the NPI-Q Nighttime Behavior Domain Severity and Caregiver Distress scores
- Change from Baseline to Week 16 on the GDS (Short Form)
- Change from Baseline to Week 16 mFSQ score by subscale

- Change from Baseline to Week 16 for each item in MDS-UPDRS Part II

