## 12.4 Handling of Missing Data

Scores that are missing, after any imputation of individual missing items as described in Section 5.2, will not be imputed. MMRM analyses will be used as the statistical approach for handling of missing data. Model parameters are simultaneously estimated using restricted maximum likelihood estimation. The MMRM method is unbiased in the estimation of treatment effect under the missing at random assumption and can be thought of as attempting to estimate the treatment effect that could have been observed if all subjects had continued on study for the full study duration.

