## 12.7 Analysis of Efficacy Endpoints

Descriptive statistics for all exploratory efficacy endpoints listed in [Section 12.3](#) will be tabulated at scheduled timepoints (excluding Screening). In addition, descriptive statistics may be provided for various subscales and individual scale items.

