## 12.8 Mixed Model Repeated Measures (MMRM)

The MMRM method with restricted maximum likelihood estimation (REML) will be used for selected efficacy endpoints. The dependent variable will be the change from Baseline. The independent variables in the model will include effects for visit, Baseline score, and Baseline score-by-visit-interaction. An unstructured covariance matrix will be used to model the within patient errors, and the Kenward-Roger approximation will be used to adjust the denominator degrees of freedom.

In the event that the model fails to converge using the unstructured covariance matrix, then only descriptive statistics will be presented.

Summary statistics (observed and change from Baseline, LS means with corresponding two-sided 95% confidence intervals (CIs), and p-values will be presented at each post-Baseline visit for the Full Analysis Set. The primary comparison is based on the LS mean change from Baseline to Week 16.

LS mean  $\pm$  SE from the MMRM model over time for the change from Baseline values will be displayed in line plots for the Full Analysis Set.

The above MMRM model will be used for each of the primary, secondary, and exploratory endpoints. CGI-I score will be analyzed using a similar MMRM model with effects for visit, Baseline CGI-S score, and Baseline CGI-S score-by-visit interaction. PGI-I score will be analyzed using an MMRM model with an effect for visit.

NPI-Q Caregiver and Distress scores will be summarized in shift tables to determine the number and percentage of subjects with Severity scores classified as none, mild, moderate, or severe relative to the same classification at the Baseline visit; and the number and percentage of subjects with Distress scores classified as not distressing at all, minimal, mild, moderate, severe, and extreme or very severe relative to the same classification at the Baseline visit. For the by-visit shift summary, the denominator is the number of subjects with non-missing values at Baseline and the given visit for the given parameter.

For each of the continuous efficacy endpoints (except for CGI-I and PGI-I) the null hypothesis is that the change from baseline to a certain time-point is equal to 0. The corresponding alternative hypothesis is that the change from baseline to a certain endpoint is not equal to 0.

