For the CGI-I and PGI-I endpoints the null hypothesis is that the score at a certain time-point is equal to 4 (no change); the corresponding alternative hypothesis is that the score at a certain time-point is not equal to 4.

For each of the continuous efficacy endpoints (except for CGI-I and PGI-I), in addition to MMRM, a paired t-test using a last observation carried forward imputation method will be performed at each post-baseline visit. For CGI-I and PGI-I, a one sample t-test (against a value of 4, indicating no change) will be performed instead of the paired t-test.

Additional exploratory analyses may be conducted on VRFCAT data to adjust for deficits in cognition.

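### NPI-Q Distress is left missing whenever nighttime behaviours are absent, so its missingness depends on the outcome and missing at random is not credible

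*SAP*

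**What the plan says.** SAP 5.2.3 rates Distress from 0 (no distress) to 5. If nighttime behaviours are reported absent, "the Severity score will be set to 0, and the Distress score will remain a missing value". Other missing ratings are not imputed.

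SAP 12.3 lists as an exploratory endpoint "Change from Baseline to Week 16 on the NPI-Q Nighttime Behavior Domain Severity and Caregiver Distress scores". SAP 12 states that "All efficacy analyses will be performed using the Full Analysis Set".

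For missing data, SAP 12.4 relies on the model: "The MMRM method is unbiased in the estimation of treatment effect under the missing at random assumption". SAP 12.8 applies that MMRM to every exploratory endpoint, with visit, Baseline score and their interaction as the only effects. It adds "a paired t-test using a last observation carried forward imputation method will be performed at each post-baseline visit". It also plans shift tables in which "the denominator is the number of subjects with non-missing values at Baseline and the given visit for the given parameter". Its fallback reads: "In the event that the model fails to converge using the unstructured covariance matrix, then only descriptive statistics will be presented".

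The only acknowledgement that Distress will be blank for some subjects is in SAP 5.1, which exempts it from the all-subject denominator for baseline percentages. Nothing restricts the change analysis to subjects with the symptom.

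**The concern.** Distress is blank because the symptom is absent, which is the best outcome a visit can record. These subjects have not left the study; they attended and the informant answered. Symptom presence is not in the Distress model, and no Distress value is ever observed at Severity 0, so the data cannot inform the model about those visits. Missing at random is not credible there.

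Three things follow if absence is read as no distress from that symptom:

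- **Resolution.** The MMRM in effect predicts a resolved visit from symptomatic ratings, LOCF copies an earlier symptomatic rating into it, and the shift table omits the subject.
- **Observed-case means.** These can move either way, depending on whether those who resolve started with low or high Distress. They are all that remains if the MMRM does not converge.
- **New onset.** Baseline Distress is missing for anyone without the symptom then, and NPI-Q is not scheduled at Screening. These subjects have no change score at any visit.

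The reported change would describe neither all caregivers nor all caregivers who began with the problem. It could not be read beside Severity, which scores absence as 0 and so keeps these subjects.

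**Working it through.** **Inputs from the documents.** Distress runs 0-5. NPI-Q is scheduled at Baseline and Weeks 2, 4, 8, 12 and 16 (SAP 20.2). Expected completers: 53 × (1 - 0.20) = 42.4, which reproduces the stated 42 (SAP 3.1). Prevalence, resolution, onset and the Distress distribution are not given; all are assumed below.

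**Step 1: by hand, comparing with absent = 0.**
- LOCF: Baseline 4, Week 12 = 3, absent at Week 16. Planned: 3 - 4 = -1. With absent = 0: 0 - 4 = -4.
- Observed-case mean: one subject goes from 1 to absent, another from 4 to 1. Planned: -3 (second subject only). With absent = 0: (-1 - 3)/2 = -2. Here the planned summary shows more improvement.

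**Step 2: subjects with a Week 16 Distress change,** 42 × prevalence × (1 - resolution):

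| Symptomatic at Baseline | Number of 42 | 10% resolve | 40% resolve |
|---|---|---|---|
| 50% | 21 | 19 | 13 |
| 70% | 29 | 26 | 18 |
| 90% | 38 | 34 | 23 |

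**Step 3: simulation.** There were 144 scenarios of 40,000 subjects. A correlated latent score at the six visits determines symptom presence (threshold) and Distress (cut-points), so earlier Distress predicts resolution. The grid was: prevalence 50/70/90%; correlation 0.3/0.6/0.8, constant or decaying; mean Baseline Distress about 2.5 or 1.6; latent improvement by Week 16 of 0, 0.3, 0.6 or 1.0 SD; 20% random drop-out. This gives 36 no-change and 108 improving scenarios. The MMRM was unstructured with the SAP's effects, fitted by maximum likelihood (close to REML at this size). Each method was compared with itself on absent = 0 data. On those data the MMRM matched the full-data value within 0.02.

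Baseline-symptomatic subjects, in the 55 improving scenarios with 10-40% resolution:

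| Method | Planned rule against absent = 0 | Median or count |
|---|---|---|
| MMRM | 6% more to 78% less improvement | median 20% less; less in 50 of 55 |
| LOCF | 2% more to 74% less | median 18% less; less in 53 of 55 |
| Observed case | 23% more to 68% less | more in 11 of 55 |

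Over all 108 improving scenarios the MMRM runs from 9% more to 86% less, and shows less in 101.

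Two examples (absent = 0 / planned MMRM / planned LOCF / observed case):
- Prevalence 70%, constant correlation 0.6, 28% resolved, mean 2.5: -0.80 / -0.29 / -0.31 / -0.38. The MMRM shows 1 - 0.29/0.80 = 64% less.
- Prevalence 90%, constant correlation 0.8, 33% resolved, mean 1.6: -1.10 / -1.14 / -0.98 / -1.35. The MMRM shows 1.14/1.10 - 1 = 4% more.

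Repeating both with different Distress cut-points gave -0.83 / -0.33 / -0.32 / -0.41 and -1.08 / -1.10 / -0.92 / -1.27.

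**Step 4: regression to the mean.** In the 36 no-change scenarios, absent = 0 gives -0.01 to -0.95 points in Baseline-symptomatic subjects but 0.00 (within 0.02) in all subjects. The planned MMRM gives -0.07 to +0.09. Part of each gap in Step 3 is therefore not missed benefit.

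**Step 5: against all subjects with absent = 0.** The planned MMRM shows more improvement in 60 of the 108 improving scenarios (by up to 0.75 points) and less in 48 (by up to 0.42).

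**Step 6: a different structure.** Here resolution and onset are set directly, do not depend on the Distress level, and there is no drop-out. Week 16 change:

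| Baseline prevalence / resolve / new onset | All subjects, absent = 0 | Planned MMRM |
|---|---|---|
| 60% / 30% / 10% | -0.59 | -0.50 |
| 60% / 50% / 5% | -0.85 | -0.47 |
| 60% / 10% / 30% | -0.18 | -0.49 |
| 40% / 20% / 30% | +0.10 | -0.29 |

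Improvement is understated where resolution dominates. Where onset dominates it is overstated, and in the last row its sign is reversed.

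**The case against.** The strongest reply is that the rule is deliberate. SAP 5.2.3 treats the two ratings differently in one sentence, and SAP 5.1 exempts Distress from a denominator. The zero level can be read as a rating of a symptom that is present. Distress would then be not applicable when the symptom is absent, and a missing-at-random objection needs a target value that the SAP never adopts.

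This stands in part. Scoring absence as 0 is a choice of what to estimate, and the instrument's scoring source is not in the documents. But the conditional reading does not rescue the plan. No section limits the change analysis to symptomatic subjects, the MMRM would predict distress from a symptom the patient does not have, and LOCF would enter a symptomatic rating at a symptom-free visit.

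Other points also stand. The scenario counts are cells in an assumed grid, not probabilities, and exact values depend on the chosen cut-points. The larger percentages use a Baseline-symptomatic comparison that is itself subject to regression to the mean. New-onset ratings still appear in observed-value summaries and listings; what they miss is the change from Baseline and the shift table. A resolved subject's earlier symptomatic visits stay in the MMRM: in the 55 scenarios only 4-11% of Baseline-symptomatic subjects had no post-baseline Distress. The Severity shift table shows resolution and onset, and the Caregiver Strain Index measures strain without this conditioning. These limit the harm but do not repair the Distress result.

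**Conclusion.** The concern holds, as a minor point. That Distress is blank when the symptom is absent, and that Baseline-asymptomatic subjects have no change score, follows from the text without any assumption. The size rests on assumed rates. Among Baseline-symptomatic subjects the planned MMRM and LOCF results generally, but not always, show less improvement than absent = 0; observed-case means go either way. Over all subjects the net direction depends on the balance of resolution and onset.

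The scope is one exploratory endpoint in a single-arm study, and SAP 12 plans no hypothesis testing. Still, SAP 12.8 presents LS means, confidence intervals and p-values for it at each post-baseline visit, so a reader will see a result whose population is undefined.

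**What to change.** In SAP 5.2.3, set Distress to 0 when nighttime behaviours are reported absent, at Baseline and every later visit. Leave it missing only when the symptom is present but unrated. Use this score in the MMRM and the LOCF t-test over all Full Analysis Set subjects. Give the Distress shift table a separate category for symptom absent, with counts of resolved and new-onset subjects. Align the Distress exception in SAP 5.1.

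If the sponsor wants an endpoint conditional on symptom presence, say so, do not carry symptomatic ratings into symptom-free visits, and report the absent = 0 analysis as a sensitivity analysis. Any result restricted to Baseline-symptomatic subjects should be supportive only, with a regression-to-the-mean caveat, because there is no control arm.

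The downside is that always-asymptomatic subjects dilute the all-subject mean, and the mean merges absent with present but not distressing; the extra shift category keeps those apart. The cost is one sentence, one derivation line, one shift-table category and two counts. No new data are needed.

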### **5.2.4 Modified Functional Status Questionnaire**

The Functional Status Questionnaire (FSQ) is a self-administered questionnaire that provides an assessment in ambulatory patients of physical, psychological, social, and role function (Jette et al. 1986). It comprises 34 core items that produce 6 summary scale scores: basic activities of daily living (ADL), intermediate activities of daily living, psychological function and mental health, work performance, social activity, and quality of interaction. In addition, it also includes 6 single-item scores: work situation; days per month in bed due to illness or injury; days per month when illness injury reduced activities normally performed for half a day or more; satisfaction with sexual relationships; satisfaction with own health; and frequency of social interaction.

Basic ADL consists of the following items:

1. Taking care of yourself, that is, eating, dressing or bathing
2. Moving in or out of a bed or chair
3. Walking indoors, such as around your home

Intermediate ADL consists of the following items:

1. Walking several blocks

2. Walking one block or climbing one flight of stairs
3. Doing work around the house, such as cleaning, light yard work, home maintenance
4. Doing errands such as grocery shopping
5. Driving a car or using public transportation
6. Doing vigorous activities such as running, lifting heavy objects or participating in strenuous sports

Social Activity consists of the following items:

1. Had difficulty visiting with relatives or friends
2. Had difficulty participating in community activities, such as religious services, social activities, or volunteer work
3. Had difficulty taking care of other people such as family members

Each of the Basic ADL, Intermediate ADL, and Social Activity items are scored as follows: 0=usually did not do for other reasons; 1=usually did not do because of health; 2=much difficulty; 3=some difficulty; 4=usually did with no difficulty.

Psychological Function consists of the following items:

1. Have you been a very nervous person
2. Have you felt calm and peaceful
3. Have you felt downhearted and blue
4. Were you a happy person
5. Did you feel so down in the dumps that nothing could cheer you up

Quality of Interaction consists of the following items:

1. Isolated yourself from people around you
2. Acted affectionate toward others
3. Acted irritable toward those around you
4. Made unreasonable demands on your family and friends
5. Gotten along well with other people

The Psychological Function and Quality of Interaction items are scored as follows: 1=all of the time; 2=most of the time; 3=a good bit of the time; 4=some of the time; 5=a little of the time; 6=none of the time.

Work Performance (for those employed during the preceding month) consists of the following items:

1. Done as much as others in similar jobs
2. Worked for short periods of time or taken frequent rests because of your health
3. Worked your regular number of hours
4. Done your job as carefully and accurately as others with similar jobs
5. Worked at your usual job but with some changes because of your health
6. Feared losing your job because of your health

The Work Performance items are scored as follows: 1=all of the time; 2=most of the time; 3=some of the time; 4=none of the time.

The modified FSQ (mFSQ) score will be calculated as the unweighted mean of the following subscale scores: Basic ADL, Intermediate ADL, Psychological Function, Social Activity, and Quality of Social Interaction. The Work performance subscale is excluded due to the age and non-employment status of the intended patient population. Prior to deriving the mFSQ total score, the following items scores are reversed: items 2 and 4 of the Psychological Function, and items 2 and 5 of the Quality of Interaction.

Subscale scores (SS, or transformed scale scores) are calculated according to this formula [[Erratum 1986](#)]:

$$SS = (100/k) \times (\text{Sum of individual item scores} - n)/n$$

Where,

n = number of questions in the subscale for which non-missing, valid information is available

k = maximum minus minimum valid response score

Activities that are not attempted because of non-health-related reasons are scored as 0 and will be excluded from average calculations [[Tedesco et al. 1990](#)]. Therefore, the maximum minus minimum valid response score for the Basic ADL, Intermediate ADL, and Social Activity will have a value of 3.

The mFSQ score will be calculated as (Basic ADL SS + Intermediate ADL SS + Psychological Function SS + Social Activity SS + Quality of Social Interaction SS)/5.

If any of the 5 subscale scores are missing then neither the mFSQ nor the subscale will be imputed.

